## **9 Sample Size Justification**

### **9.1 Primary Effectiveness Endpoint**

The primary effectiveness endpoint is freedom from documented atrial tachyarrhythmia recurrence without failure modes during the evaluation period (Day 181-450). A performance goal of 40% is set for the primary effectiveness endpoint. Please refer to Section 4.1 of the protocol for justifications of performance goals for the primary effectiveness endpoint.

Based on a performance goal of 40% and an anticipated freedom from AF recurrence rate of 50%, 330 subjects will be required to obtain at least 90% power at a two-sided significance level of 0.05 using the exact binomial method.

### **9.2 Primary Safety Endpoint**

The primary safety endpoint is the incidence of any primary adverse event occurring within 7 days of the AF ablation procedure (including the initial and repeat AF ablation procedure) using the study catheter. A performance goal of 16% is set for the primary safety endpoint. Please refer to Section 4.1 of the protocol for justifications of performance goals for the primary safety endpoint.

Based on a performance goal of 16% and an anticipated rate of 8% for the primary safety endpoint, 232 subjects will be required to obtain at least 90% power at a two-sided significance level of 0.05 using the exact binomial method.

### **9.3 Total Sample Size**

It is estimated that the attrition rate is no more than 10%. In order to obtain 330 subjects, Biosense Webster proposes to enroll 367 ( $=330/0.90$ ) subjects to account for this potential subject attrition.

## **10 Statistical Analysis Methods**

### **10.1 General Conventions**

- Descriptive statistics for categorical variables will include frequency and percentage. If not otherwise specified, the percentages will be calculated as the number of subjects or events divided by the total number of subjects or events with non-missing data in the specified analysis population. In the calculation of the percentage of subjects having a specific adverse event, the subject will only be counted once even if the subject had the same adverse event multiple times.

- The 95% confidence intervals for proportions will be exact if not otherwise specified.
- The distribution of categorical variables will be compared across multiple groups using the Fisher's exact test.
- Descriptive statistics for continuous variables will include at a minimum, number of subjects, mean, standard deviation, median, minimum and maximum.
- The distribution of continuous variables will be compared across multiple subgroups using Analysis of Variance (ANOVA) or Kruskal-Wallis test depending on the distribution of the variables.
- The Study Day (the number of days since the initial ablation) will be calculated as:

$$\text{Study Day} = \text{date of the occurrence of event} - \text{initial ablation date}$$

Note: The day of initial ablation is considered Study Day 0. The "event" in the above definition includes: recurrence of atrial tachyarrhythmias, onset of AEs, etc.

- The first 3 months post the ablation procedure is defined as the 3-Month Medication Adjustment Period (Day 0-90), while the following 3-month period is defined as the 3-Month Therapy Consolidation Period (Day 91-180).
- Age is the number of years between the year of birth and the date of informed consent form signed and will be calculated as the integer value of (*year of informed consent signed* – *year of birth*).

## 10.2 Subject Disposition

- **Enrolled Subjects:** subjects who sign the informed consent.
- **Excluded Subjects:** subjects who are enrolled but never undergo insertion of the study catheter.
- **Discontinued Subjects:** subjects have the investigational catheter inserted but do not undergo ablation (ie, no RF energy is delivered via the study device). These discontinued subjects will be followed up for 30 days.
- **Lost to Follow-up Subjects:** subjects who are enrolled and have study catheter inserted, but contact is lost after most recent follow-up visit (despite 3 documented attempts).
- **Withdrawn / Early Termination Subjects:** subjects who withdraw consent for study participation or are withdrawn by the investigator or are terminated from the study prior to completion of all follow-up visits.

- **Completed Subjects:** enrolled subjects who completed the 15-month follow-up visit.

Subject accountability and disposition will be summarized descriptively in all enrolled subjects.

### **10.3 Demographics and Baseline Characteristics**

Demographic and baseline characteristics will be summarized for all enrolled subjects overall and by sex. Demographic and baseline characteristics will also be summarized for subjects in the safety, mITT, and per protocol populations.

### **10.4 Primary Endpoints Analyses**

#### **10.4.1 Primary Effectiveness Endpoint**

The primary effectiveness endpoint is defined as achieving effectiveness success at 12 months after undergoing an RF ablation procedure using the THERMOCOOL® SMARTTOUCH™ SF catheter. The primary effectiveness rate will be compared to a pre-determined performance goal of 40%.

The primary effectiveness endpoint will be evaluated by constructing the two-sided 95% exact confidence interval for the effectiveness rate. If the lower bound of the exact confidence interval of the primary effectiveness endpoint rate is greater than the performance goal of 40%, the study will be considered to have demonstrated effectiveness of the device.

The per protocol population (PP) will be used as the primary analysis population for effectiveness. Subjects with missing effectiveness data during the 15-month follow-up period will be excluded from the primary analysis.

Analyses of the primary effectiveness endpoint will be repeated using the mITT population. Subjects with catheter inserted but no RF delivered due to investigational device deficiency in the mITT population will be categorized as effectiveness failures and included in the analysis. Subjects with no RF delivery due to other reasons (e.g. anatomical difficulty, complications) will be excluded from the mITT analysis and be included in the sensitivity analysis for missing data.

Sensitivity analyses for missing data will be performed using the PP and mITT populations to assess the impact of missingness on the primary effectiveness outcome and are outlined in section 10.4.3.

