3.2 Subject Disposition

- **Enrolled Subjects:** subjects who sign the informed consent.
- **Excluded Subjects:** subjects who are enrolled but never undergo insertion of the study catheter.
- **Discontinued Subjects:** subjects who have the investigational catheter inserted but do not undergo ablation (i.e., no RF energy is delivered via the study device). These discontinued subjects will be followed up for 30 days.
- **Lost to Follow-up Subjects:** subjects who are enrolled and have study catheter inserted, but contact is lost after most recent follow-up visit (despite 3 documented attempts).
- **Withdrawn / Early Termination Subjects:** subjects who withdraw consent for study participation or are withdrawn by the investigator or are terminated from the study prior to completion of all follow-up visits.
- **Completed Subjects:** enrolled subjects who completed the 15-month follow-up visit.

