5.11 Post Procedure Assessments

- Before hospital discharge:
 - Occurrence of arrhythmias, if any
 - Electrocardiogram (12-Lead ECG)
 - NIH Stroke Scale (NIHSS) assessment prior to hospital discharge
 - Transthoracic Echocardiogram (TTE), if necessary. Subjects who develop symptoms suggestive of pericardial effusion and/or pericarditis should undergo a transthoracic echocardiogram (TTE) to assess the pericardium, before hospital discharge. In the event significant pericardial effusion is identified, subjects should be followed until the condition resolves.
 - Cardiac-related concomitant medications (such as AADs, anticoagulation regimen, etc.)
 - Adverse events, if any
 - Collect Subject Hospitalization Billing information (including UB04 and EOB)
- Follow-up measurements at **7-9 Days (telephone), 1-Month (30 +/- 7 days, telephone or office visit)** and **3-Month (90 +/- 7 days; office visit)**:
 - Adverse events, if any
 - Subjects who have symptoms suggestive of PV stenosis should undergo imaging (CT/MRI)
 - Health Economic Data for hospitalizations, ER visits and outpatient visits, if any
 - At all visits, health economic data to be collected may include, but is not limited to: hospitalization charge (UB04), repeat ablation procedure and/or procedures resulting from the ablation procedure, outpatient visits, and ER visits

- **Follow-up measurements at 6-Month (180 +/- 14 days), 9-Month (270 +/- 28 days), 12-Month (360 +/- 28 days) and 15-Month (450 +/- 28 days) Clinic Visits:**
 - Medical / Hospitalization History
 - Occurrence of arrhythmias, if any
 - Electrocardiogram (12-Lead ECG)
 - QOL Assessments (AFEQT and AF Symptom Frequency and Severity Checklist)
 - 24 Hour Holter Monitor (6, 12 and 15-Month)
 - TTM Monitor (monthly transmissions starting 7 months post procedure and when symptomatic cardiac episodes occur)
 - Concomitant medications only cardiac related (AADs, anticoagulation regimen, etc.)
 - Adverse events, if any
 - Subjects who have symptoms suggestive of PV Stenosis should undergo imaging (CT/MRI)
 - AF Recurrence
 - Health Economic Data for hospitalizations, ER visits and outpatient visits, if any
 - At each follow-up visit, health economic data to be collected may include, but is not limited to: hospitalization charge (UB04), repeat ablation procedure and/or procedures resulting from the ablation procedure, outpatient visits, and ER visits
 - End of Study Report (15-Month)

Figure 5-2 Study Flow Diagram

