⁸ AEs collected once consent has been signed

⁹ If AE results in Hospitalization health economic data collection is required

¹⁰ Collected via phone follow-up

¹¹ PV imaging (CT/MRI) for subjects who have symptoms suggestive of PV stenosis

¹² Performed prior to hospital discharge or 24 hours after the procedure, whichever is later or any time after the subject experiences a CVA/Stroke, perform Neuro consult as needed Refer to section 6.2.1 for additional details.

¹³ Asymptomatic TTM: should be recorded monthly (i.e. at months 7, 8, 9, 10, 11, 12, 13, 14, 15) and transmitted to the Core Lab. Refer to section 5.15.

¹⁴ TTM: all symptomatic cardiac episodes should be recorded and transmitted at the time the event occurs. Refer to section 5.15.

¹⁵ 15-month visit or last completed visit

¹⁶ Subjects who develop symptoms suggestive of pericardial effusion and/or pericarditis should undergo a transthoracic echocardiogram (TTE) to assess the pericardium

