7.2 Analyses for Primary Endpoints

7.2.1 Analyses for Primary Effectiveness Endpoint

The null and alternative hypotheses are:

Hypothesis $H_0: P_E \leq 0.40$

$H_a: P_E > 0.40$

P_E : the freedom from documented atrial fibrillation, atrial flutter and atrial tachycardia recurrence at 15 months follow-up

Null hypothesis: The freedom from documented AF/AFL/AT at 15 months is less than or equal to the pre-determined performance goal of 40%.

Alternative hypothesis: The freedom from documented AF/ATL/AT at 15 months is greater than the pre-determined performance goal of 40%.

Analysis Population: The per-protocol population will be used as the primary analysis population. Subjects with missing effectiveness endpoints data during 15 months follow-up period will be excluded from the primary analysis. The subjects who have failed the primary effectiveness endpoint before 15 months will be included in the analysis. Analyses of the primary effectiveness endpoint will be repeated in the mITT population. Sensitivity analyses for missing data will be performed in the PP and mITT populations to assess the impact of missingness on the primary effectiveness outcome and are described in the Statistical Analysis Plan (SAP).

Analysis Method: The primary effectiveness endpoint will be evaluated using the exact test for a binomial proportion at a two-sided significance level of 5%. If the lower bound of the exact two-sided 95% confidence interval of the primary effectiveness endpoint rate is greater than the performance goal of 40%, the study will be considered to have demonstrated effectiveness.

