### **6 Study Endpoints**

#### **6.1 Primary Endpoints and Associated Hypotheses**

##### **6.1.1 Primary Effectiveness Endpoint**

The primary effectiveness endpoint is defined as achieving effectiveness success after undergoing an RF ablation procedure using the THERMOCOOL® SMARTTOUCH™ SF catheter.

The null and alternative hypotheses are:

*Hypothesis:*  $H_0: P_E \leq 0.40$

$H_a: P_E > 0.40$

where  $P_E$  is the proportion of subjects who meet the effectiveness success criteria at 15 months follow-up

A subject has reached the effectiveness success if the subject is free from documented atrial tachyarrhythmia, including atrial fibrillation, atrial flutter and atrial tachycardia (AF/AFL/AT), recurrence (episodes  $\geq 30$  secs on Holter recordings/TTM or continuously recorded on the standard 12-leads ECG) during the evaluation period (Day 181-450) and free from the following failure modes:

- Acute procedural failure, including
  - Failure to confirm entrance block in all pulmonary veins post-procedure,
  - Use of a non-study catheter to treat the study arrhythmia for initial ablation,

- Non-study catheter failure while treating the study arrhythmia for repeat ablation procedure during the 3-Month Medication Adjustment or 3-Month Therapy Consolidation Period
- Repeat ablation failure, including
  - >2 repeat ablation procedures during the 3-Month Medication Adjustment Period / 3-Month Therapy Consolidation Period (Day 0-180) after the index procedure,
  - Any repeat ablation procedure during the evaluation period.
- AAD failure: Taking a new AAD or a previously failed AAD at a greater than the highest ineffective historical dose for AF during the evaluation period.
- Surgical failure: Undergoing surgical AF ablation or AF surgery any time after the index procedure.

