##### *2) Worst-Case Scenario*

Subjects with missing effectiveness outcome will be treated as effectiveness failure. The point estimate for freedom from recurrence of atrial tachyarrhythmias and the exact two-sided 95% confidence interval will be presented.

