##### **10.5.1.2 15-Month Single Procedure Success**

The following analyses will be performed in the PP population:

- The 15-month single procedure success will be presented treating the endpoint as a binary variable. The point estimate and the corresponding two-sided 95% confidence interval will be presented.
- Kaplan-Meier analysis: this analysis will include all subjects in the PP population. Subjects with less than 15-month follow-up will be censored at their last observations.

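### Does the plan need a definition of 'missing' before event-free subjects can be excluded from the primary effectiveness analysis?

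*SAP*

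**What the plan says.** The primary effectiveness endpoint is binary. Success means no documented AF, AFL or AT on Day 181-450 and none of the listed failure modes (Protocol 4.1.1, SAP 6.1.1). The primary analysis uses the per-protocol population, and the goal is met if the exact two-sided 95% lower bound exceeds 40%.

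On missing outcomes, SAP 10.4.1 says: "Subjects with missing effectiveness data during the 15-month follow-up period will be excluded from the primary analysis". Protocol 7.2.1 has the same exclusion and adds: "The subjects who have failed the primary effectiveness endpoint before 15 months will be included in the analysis".

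The nearby definitions serve other purposes:

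- Protocol 3.2 defines completed subjects as "enrolled subjects who completed the 15-month follow-up visit", a disposition category.
- A footnote to Protocol Table 5-1 lets the end-of-study entry be the "15-month visit or last completed visit".
- SAP 10.5.1.2 says "Subjects with less than 15-month follow-up will be censored at their last observations", but for the Kaplan-Meier analysis of a secondary endpoint.
- SAP 10.4.3.1 sets out what to do with a missing outcome. In the worst case, for example, "Subjects with missing effectiveness outcome will be treated as effectiveness failure". It does not say when an outcome is missing.

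**The concern.** An event-free subject is a success only because nothing was found, so how much looking was done matters. Apart from the 6-month visit, 14 rhythm recordings are scheduled for the Evaluation Period, and partial records are to be expected. Taken literally, missing data could mean one missed transmission, no 15-month visit, or no recording at all after Day 180.

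The visit windows add to this. Protocol 5.11 allows "15-Month (450 +/- 28 days) Clinic Visits", that is Day 422-478, so an on-time final ECG and Holter can fall after the counting window closes on Day 450.

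The definition sets both the numerator and the denominator of the primary result. The best-case, worst-case, imputation and tipping-point analyses act only on subjects already labelled missing. A sparsely monitored subject labelled a success stays a success in all of them. The study is single-arm and unblinded, so a definition chosen late could be chosen with the result in view.

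**Working it through.** **Inputs.** Goal 40%, anticipated rate 50%, N = 330 for at least 90% power, two-sided 5% exact test (SAP 7 and 9.1). Attrition at most 10%, 367 enrolled (SAP 9.3). Recordings from Protocol 5.11, 5.15 and Table 5-1.

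**The plan's own figure.** The lower bound L(x, n) is the 2.5% quantile of Beta(x, n - x + 1). The goal is met when L > 0.40.

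- n = 330: L(150) = 0.3999 fails and L(151) = 0.4029 passes. P(X >= 151) is 0.019 at 40% and 0.945 at 50%, so at least 90% power is true.
- 330/0.90 = 366.7, rounded up to 367.
- n = 367: L(165) = 0.3979 fails and L(166) = 0.4006 passes.

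**Recordings and windows.** 9 monthly TTM + 3 ECG (months 9, 12, 15) + 2 Holter (months 12, 15) = 14. The 15-month window has 478 - 422 + 1 = 57 days, of which 478 - 450 = 28 fall after Day 450.

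**What the protocol implies.** If short follow-up did not already mean exclusion, the sentence in Protocol 7.2.1 that keeps early failures in would be unnecessary. So an event-free subject who leaves early is most naturally excluded and passes to SAP 10.4.3.1. The open case is narrower: subjects who reach 15 months with gaps, or with the last recordings made on Day 451-478.

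**The extreme contrast.** Suppose 367 subjects are analysed, m of them event-free with partial records, and S ~ Bin(367 - m, p) successes occur among the rest. If the m are excluded, S must reach the exact cutoff for 367 - m. If the m are counted as successes, S must reach 166 - m.

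| m | S needed, excluded | S needed, counted | P(pass) at 40%: excluded / counted | at 45% | at 50% |
|---|---|---|---|---|---|
| 4 | 165 of 363 | 162 | 2.0% / 4.1% | 45.1% / 57.7% | 96.3% / 98.2% |
| 18 | 159 of 349 | 148 | 2.0% / 19.4% | 43.7% / 84.8% | 95.7% / 99.8% |
| 37 | 151 of 330 | 129 | 1.9% / 65.2% | 41.2% / 98.7% | 94.5% / 100.0% |

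The verdict differs for 165 - 162 = 3, 159 - 148 = 11 or 151 - 129 = 22 values of S. At 50% the chances differ by 1.9, 4.1 and 5.5 percentage points. One split result: 140/330 = 42.4% has lower bound 37.0% and fails, while (140 + 37)/367 = 48.2% has lower bound 43.0% and passes.

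**A less extreme model.** Assume, since the documents do not say, that a random 10% of 367 drop out and half of the dropouts' failures are seen first.

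- True rate 40%: event-free dropouts are 0.10 x (1 - 0.60 x 0.5) = 0.070 and observed successes 0.40 x 0.90 = 0.360. Excluding the dropouts gives 0.360/0.930 = 38.7% and passes 0.7% of the time. Counting them gives 43.0% and passes 20.9%.
- True rate 50%: 0.075 and 0.450. Excluding gives 0.450/0.925 = 48.6% and passes 89.3%. Counting gives 52.5% and passes 99.8%.

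Under these assumptions exclusion works against the device and does not inflate the error rate.

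**Would tying evaluability to the 15-month visit help?** Take a rule that accepts any event-free subject with an ECG or Holter at an in-window 15-month visit.

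- A subject whose only recording is an ECG on Day 470 becomes an evaluable success with nothing recorded in Day 181-450, and is never tested in the worst case or tipping point. If that ECG shows AF, the primary result is still a success.
- A subject with nine TTM transmissions, 9- and 12-month ECGs and a 12-month Holter, but no 15-month visit, becomes missing.

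**The case for a change.** The strongest objection is that the definition is absent, the trial is unblinded, and the planned sensitivity analyses cannot reach a subject already labelled a success. All three statements are true. Even 4 subjects double the chance of passing at a true 40% rate (2.0% to 4.1%), the differences at 45% are large, and a sentence in the SAP would cost little.

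Three things limit what this shows. First, the arithmetic compares excluding early leavers with counting them as successes, and the protocol points to exclusion. The subjects whose status is really open, completers with gaps, are not modelled, and their number is not in the documents. Second, 367 overstates the per-protocol set, because enrolment means signed consent and that set also needs eligibility and ablation with the study catheter. The case m = 37 also gives the entire attrition allowance to one subgroup. Third, SAP 10.4.5.2 plans a Kaplan-Meier estimate of recurrence at 15 months in both populations, with censoring and a 95% interval, which uses partial follow-up without any missing label. It is exploratory and covers recurrence only, so it softens the gap without closing it.

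What stands is that the SAP leaves to the analyst how much monitoring within Day 181-450 supports a success.

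**Conclusion.** No change to the plan is called for. The wording gap is real, but it is missing detail: no stated rule gives a wrong result. The window, the test, the treatment of early failures and the handling of missing outcomes are all fixed, and an evaluability rule has to be written to build the endpoint in any case. Late 15-month visits affect how completely recurrences are detected, not which days count.

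The size cannot be derived from the documents. The 65% figure is an extreme from an unlikely reading. At the planned 50% rate that same reading changes the chance of passing by 1.9 to 5.5 points.

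This rests on two assumptions: that event-free subjects with short follow-up are excluded, as Protocol 7.2.1 implies, and that the derivation is settled without reference to the result. If the second failed and the observed rate lay close to the cutoff (151 of 330, 45.8%), the definition could decide the outcome.

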### 8 Analysis Sets

For the analysis of study endpoints, the analysis populations are defined as the following:

- **Modified Intent-To-Treat (mITT) Population:** the mITT population will consist of all enrolled subjects who meet all eligibility criteria AND in whom
  - (1) RF energy was delivered with study catheter OR
  - (2) Study catheter was inserted but no RF energy was delivered
- **Safety Population (SP):** The safety population will consist of all enrolled subjects who have undergone insertion of the study catheter. Safety endpoints will be analyzed based on the Safety Population.
- **Per Protocol (PP) Population:** The PP population will include subjects who satisfy the following criteria:
  - are enrolled and meet all eligibility criteria
  - have undergone RF ablation
  - are treated with the study catheters, and have been treated for the study-related arrhythmia

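### SAP 10.4.1 drops inserted/no-RF subjects from the supportive mITT analysis unless the study device was at fault, although the endpoint's failure modes do not exempt the other causes it names

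*SAP*

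**What the plan says.** **Who is in mITT.** SAP 8 and Protocol 7.1 admit eligible subjects who received RF from the study catheter and also those for whom "2) Study catheter was inserted but no RF energy was delivered". Neither sets a condition on the cause.

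**How they are scored.** SAP 10.4.1 says that subjects with no RF "due to investigational device deficiency in the mITT population will be categorized as effectiveness failures and included in the analysis". For every other cause it says: "Subjects with no RF delivery due to other reasons (e.g. anatomical difficulty, complications) will be excluded from the mITT analysis". Those subjects go to the missing-data sensitivity analyses of SAP 10.4.3.1. No reason for the split is given.

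**What counts as failure.** SAP 6.1.1 and Protocol 4.1.1 list acute procedural failure, which includes "Failure to confirm entrance block in all pulmonary veins post-procedure" and "Use of a non-study catheter to treat the study arrhythmia for initial ablation". Only Protocol 4.1.1 states an exemption: a deficiency of a non-investigational device (generator or pump) that leads to use of a non-study catheter.

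**Role of the analysis.** PP is the primary population and requires RF ablation, so no-RF subjects are never in it. Protocol 7.2.1 adds only that "Analyses of the primary effectiveness endpoint will be repeated in the mITT population". No success criterion is attached to that repeat.

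**Follow-up.** SAP 10.2 and Protocol 3.2 follow inserted/no-RF (Discontinued) subjects for 30 days. The evaluation period is Day 181-450.

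**The concern.** The mITT repeat is there to show whether the PP result survives when subjects whom PP leaves out are put back. Those with an attempted procedure and no RF are the clearest such group. SAP 10.4.1 puts back only the part attributed to the study device and removes the rest again.

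The removed subjects are not ordinary missing data. A case aborted with no ablation ends without confirmed entrance block. A case completed with another catheter meets the non-study-catheter failure mode. Either way the endpoint lists a failure, and anatomy and complications are not exempt. Their outcome in the evaluation period will never be observed, by design.

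At stake is the headline mITT rate. Leaving out failures moves it one way only, up and toward PP, which weakens it as a check on PP.

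**Working it through.** **Inputs.** Goal 40%, anticipated rate 50%, 330 evaluable subjects, two-sided 5%, exact binomial (SAP 7, 9.1). Pass if the exact 95% lower limit exceeds 40% (SAP 10.4.1). Attrition 10% (SAP 9.3). The number *k* of no-RF subjects with other causes is not in the documents; I assume 3 to 10.

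**1. The plan's own figure.** The lower limit is 39.99% for 150/330 and 40.29% for 151/330, so 151 successes are needed. With X binomial (330, 0.50), P(X ≥ 151) = 94.5%, which meets the stated minimum of 90%. Enrolment is 330/0.90 = 366.7, rounded up to 367. Nothing below changes these figures.

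**2. Shift in the mITT rate.** With *x* successes in *n* RF-treated subjects, exclusion gives x/n and failure scoring gives x/(n+k). The difference is (x/n) × k/(n+k).

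| | Rate | Exact lower limit | Shift |
|---|---|---|---|
| Excluded, 165/330 | 50.0% | 44.5% | – |
| k = 3, 165/333 | 49.5% | 44.1% | 0.50 × 3/333 = 0.45 points |
| k = 10, 165/340 | 48.5% | 43.1% | 0.50 × 10/340 = 1.47 points |

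All three pass. If the 10 are instead counted inside an mITT set of 330, the comparison is 160/320 = 50.0% (lower limit 44.4%) against 160/330 = 48.5% (43.0%), the same shift.

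**3. What the planned sensitivity analyses do with them (k = 10, no other missing data).**
- Best-case: (165+10)/340 = 51.5%. Never-ablated subjects count as successes.
- Multiple imputation: about (165+5)/340 = 50.0% if they are imputed at the treated subjects' rate. The model uses demographic and baseline covariates that are not fully named, so this holds unless those covariates separate the groups.
- Worst-case: 165/340 = 48.5%, the failure-scored result.
- Tipping-point: reaches the same result once all 10 have been replaced by failures.

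In the real analysis the last two also contain subjects lost before 15 months. At 165 successes among 330 observed, worst-case passes with 35 missing (165/365, lower limit 40.02%) and first fails with 36 (165/366, 39.91%). A failing row would not show which kind of missing subject caused it.

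**4. When the mITT conclusion would reverse.** The minimum passing count is 151 of 330, 152 of 333 and 155 of 340. So with k = 3 only an observed count of 151 reverses (151/333, lower limit 39.91%). With k = 10 the counts 151 to 154 reverse (154/340, 39.92%). At a true 50% in the 330, the chance of landing there is 1.3% and 6.9%. Equivalently, the chance that the mITT lower limit exceeds 40% goes from 94.5% to 93.1% (k = 3) or 87.6% (k = 10).

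**The case against.** **The endpoint may presuppose ablation.** SAP 6.1.1 words success as following an RF ablation procedure, so a never-ablated subject could be called not evaluable. A device study could also reasonably charge the device with its own failures and set other aborted cases aside. That is a coherent choice of estimand, but it is nowhere stated. If ablation were a precondition, the device-deficiency cases would drop out too, and SAP 10.4.1 keeps them.

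**Much of this is already visible.** That stands. Worst-case scores these subjects as failures, the tipping-point table covers every split of the missing outcomes, reasons for missingness are listed by site where available, and discontinued subjects are reported. A reader with the no-RF count could approximate the result. The headline mITT rate, the best-case row and the imputed rate would still not show it.

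**The group may be small.** That also stands. mITT requires eligibility, and exclusion criteria 28 and 29 already cover some problems of access or catheter manipulation, so some anatomical cases would be outside mITT under any rule.

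**A breach of the protocol might be inferred.** Protocol 7.2.1 says: "The subjects who have failed the primary effectiveness endpoint before 15 months will be included in the analysis". That sentence sits with the PP primary analysis and its missing-data rule, and reaches mITT only because the analysis is to be repeated there. It does not say how to score no-RF subjects, so it does not support a claim that the SAP breaks a protocol rule.

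**Inflated type I error might be inferred.** If the rate with no-RF subjects as failures were exactly 40% (N = 340, 10 of them no-RF), the mITT limit would pass with probability 5.3% under exclusion and 2.0% under failure scoring. Since no success criterion rests on mITT, this is not trial-level error, and it takes the top of an assumed range.

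**Conclusion.** The point holds for the supportive mITT analysis. SAP 10.4.1 handles as missing a group whose outcome the endpoint's failure modes already describe, and the effect is in one direction. The size is modest: about 0.5 to 1.5 percentage points at the planned rate, with a reversed mITT conclusion only within a few successes of the threshold. This rests on the assumed 3 to 10 eligible subjects and on reading the failure modes as applying to an attempted procedure without RF.

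Two stronger conclusions might be drawn, and the documents support neither. The first is that the trial's effectiveness decision is biased; that decision rests on PP, which these subjects never enter. The second is that every no-RF subject must be a failure without exception; the Protocol 4.1.1 exemption could reach a subject whose generator or pump failed and who was then treated with another catheter.

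PP and mITT may also differ for another reason, since PP requires that subjects "are treated with the study catheters, and have been treated for the study-related arrhythmia". A gap between the two rates should therefore not be put down to no-RF cases alone. The change is worth making because it is cheap, not because the trial depends on it.

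**What to change.** In SAP 10.4.1:

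- Score eligible inserted/no-RF mITT subjects as effectiveness failures regardless of cause. Except the case that Protocol 4.1.1 exempts (a non-investigational device deficiency leading to a non-study catheter), which stays as missing.
- Keep the scored failures as failures in the mITT best-case, imputation and tipping-point runs. Worst-case needs no change.
- Show the current device-attributable rule as a sensitivity row.

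In SAP 10.2, split the Discontinued line by reason: investigational device deficiency, the exempted case, other.

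The cost is a short rewording of 10.4.1, one split disposition line and one extra row. The supportive mITT rate becomes slightly less favourable and will count some no-RF cases that the device did not cause; the sensitivity row shows how much of the difference they explain. The PP analysis, alpha and the sample size of 330 (367 enrolled) stay as they are.
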